The primary outcome measure is pain score at 24 hours, which will be obtained by phone follow up. Secondary outcomes include maximal pain score on postoperative day 1, 2 and 3, total oral opioid morphine equivalent after 3 days, and occurrence of typical opioid side effects (nausea, vomiting, and/or drowsiness). In addition to follow up phone call on POD 1, patients will keep a pain diary, documenting pain scores and opioid use for the first 72 hours, which will be collected by the surgeon in his office at the first postoperative visit. Any adverse occurrences related to nerve blockade or prolonged bupivacaine effect will also be recorded. In addition, the development of chronic pain at the surgical site will be assessed and compared between the two groups, with appropriate referral to the chronic pain service for any patient who experiences this outcome.

Study Design and Methods:

This randomized, double blind, placebo-controlled study was approved by the University of Pittsburgh Institutional Review Board (PRO17020089), and registered with ClinicalTrials.gov (NCT03149887).

Patients will provide written consent for participation on the day of surgery. A computer-generated randomization number will be assigned by the Investigational Drug pharmacy at our institution, and patients will be accordingly designated to receive either liposomal bupivacaine or normal saline injection. The pharmacy will then prepare the study drug (either liposomal bupivacaine or saline), packaged in a fashion that cannot be recognized by the investigators, and then sent to the operating room for injection by the surgeon.

The patients and the research team will be blinded to which group the patients are in. It is not possible to prepare an effective placebo solution for the liposomal bupivacaine, so the surgeon will remain un-blinded. Other members of the research team will determine the primary and secondary outcomes, and the

surgeon will not take part in the data collection for primary or secondary analyses. By the time of the first surgical follow up examination, the outcomes will have been determined and recorded by investigators.

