All patients will undergo standard interscalene nerve blocks with plain bupivacaine 0.5% or ropivacaine 0.5%, with volumes varying between 15 and 20 ml based upon visual analysis of injectate spread by the anesthesiology team. Once an effective nerve block is demonstrated (inability to raise the arm, biceps weakness, loss of sensation over the C4 and C5 dermatome regions), patients are to be taken to the operating room. Anesthesia for the procedure will consist of the interscalene nerve block, along with infusion of propofol for sedation, accompanied by small doses of ketamine (20 to 40 mg), and dexmedetomidine (12-20 mcg).

Per our institutional review board, it is essential that the joint capsule be closed before injection of liposomal bupivacaine, since liposomal bupivacaine is not approved for intra-articular use. If the capsule cannot be closed for surgical reasons at the end of the procedure, an enrolled patient will be removed from the study at that point, and will not receive the injection of the study drug. The rotator cuff repairs are to be performed in the beach chair position by a single surgeon with either three or four routine portals, including anterior, posterior, and one or two lateral portals. The total dose of liposomal bupivacaine will be 266 mg, diluted with an additional 40 ml of saline to a total of 60 ml. In control patients, 60 ml of normal saline are to be injected in like fashion. In each group, the sixty milliliters of solution was divided into two thirty milliliter syringes. After completion of the arthroscopic rotator cuff repair, which includes a subacromial decompression, an eighteen gauge spinal needle will be placed under direct vision into the subacromial space and secured with tape. The arthroscopic instrumentation will be removed and each of the three or four portals then infiltrated at the superficial skin and the deep tissue, including the deltoid muscle surrounding the portal tract, with equally divided amounts from one of the thirty milliliter syringes using a one and one-half inch twenty-two gauge needle. The portals will then be closed with absorbable suture and the remaining thirty milliliters of solution in the second syringe injected into the subacromial space via the previously placed eighteen gauge spinal needle. Finally, the needle is to be removed, and the dressings as well as a sling are applied.

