At the conclusion of surgery, patients will be taken to PACU, where they report their NRS pain score, and intravenous dilaudid will be provided for analgesia for scores greater than 3/10. Patients are to be called the day after surgery (approximately 24 hrs after leaving the hospital), and asked about their pain experience. Specifically, for the primary outcome, they will be asked to relate NRS pain score, at the time that the interscalene block had, in their perception, completely resolved (restoration of hand sensation, movement at elbow, and onset of pain at the shoulder). For the secondary analyses of pain and opioid use, patients will record their NRS scores in a 72 hour postoperative diary, for pain at rest and (for patients instructed to do so) when participating in range-of-motion exercises ("pendulum swings"). In addition, the participants are to record oral opioid doses, use of other analgesics (such as acetaminophen), and any side effects that they encounter. Patients also will rate their satisfaction regarding pain management at the end of the 72 hour period. The pain diary will then be brought to the one-week follow up appointment, collected by the research team, and the data transcribed. Finally, the surgeon will note any patient who develops chronic pain requiring referral to a pain management specialist.

Eligibility Criteria:

Those eligible for inclusion are adults ages 18-65, in American Society of Anesthesiologist physical status class 1 through 3, who are undergoing arthroscopic rotator cuff repair, either primary or revision. Exclusion criteria include pre-existing nerve damage, pre-existing chronic pain in the shoulder joint, opioid use for greater than 30 days preoperatively, coagulopathy, renal or liver disease, pregnancy, allergy

to local anesthetics, patient refusal, infection at the site of injection, age over 65 years, or incompetent rotator cuff/joint capsule.

Statistical Considerations:

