Sample size is calculated based on the a priori assumption that liposomal bupivacaine would result in a reduction of pain scores at the time of block resolution by two or more units in the NRS rating (0 to 10 scale). The minimum clinically important difference for acute pain, acute postoperative pain, and shoulder-related pain range between 1 and 2 (out of 10), We chose a change in the score of 2 units to represent a clinically important improvement in pain control. To detect a decrement of 2 units or more with a two-tailed significance level of 0.05 and a power of 0.8, a sample size of 50 is required, 25 in each group.

The analysis of data will be carried out using SAS software, Version 9.4, of the SAS System for Windows (Copyright 2016 SAS Institute Inc., Cary, NC, USA). Continuous measures, such as pain scores, oral morphine equivalents, and some demographic information, are presented as mean \pm standard deviation, and compared using t-tests. Frequency distributions of categorical variables, such as opioid related side effects, and other demographic information, are compared using the Fisher's exact test. Opioid use will be converted to oral morphine equivalents. A two-tailed p value of <0.05 is considered to reflect statistical significance, while a difference in the primary outcome of 2 or more on the NRS scale is our threshold for clinically meaningful change

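### The block may be either of two drugs and the primary score is timed by block resolution, but block drug enters neither the randomisation nor the analysis: a modest, cheaply avoided loss of balance and precision

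*Combined protocol and SAP*

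**What the plan says.** **Block.** Study Design and Methods allows "standard interscalene nerve blocks with plain bupivacaine 0.5% or ropivacaine 0.5%, with volumes varying between 15 and 20 ml". Volume is set from the spread seen in each patient: "with volumes varying between 15 and 20 ml based upon visual analysis of injectate spread by the anesthesiology team". For the drug, no selection rule is given.

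**Primary outcome.** Study Design and Methods ties it to the block: "for the primary outcome, they will be asked to relate NRS pain score, at the time that the interscalene block had, in their perception, completely" (the sentence goes on to say resolved). Statistical Considerations powers the trial on the same moment, assuming that the study drug "would result in a reduction of pain scores at the time of block resolution by two or more units in the NRS rating". Study Objectives differs: "The primary outcome measure is pain score at 24 hours, which will be obtained by phone follow up".

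**Randomisation.** The description is "A computer-generated randomization number will be assigned by the Investigational Drug pharmacy at our institution". No stratification factor is named.

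**Analysis.** Statistical Considerations compares continuous measures, including pain scores, by t-tests and names no covariate. Block drug and volume appear nowhere as a stratification factor, covariate or subgroup, and recording them is not mentioned.

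**The concern.** Block drug is closer to the primary outcome than an ordinary background variable. Under the block-resolution definition, the block sets when pain is scored and how long after the study injection that falls. Under the 24-hour definition, it sets how long the patient has been without a block when scored. If the two drugs differ in duration, or in pain as they wear off, that difference adds to the spread of the primary score. In a trial of 25 per arm it can also fall unevenly between the arms by chance.

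The block precedes the study injection, which is given after the repair is complete, so block drug is a factor that could be balanced or adjusted for. As written, the plan does neither. Unless the drug is recorded, a reader of the result could not check whether the arms were comparable on it.

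**Working it through.** **Inputs from the document (Statistical Considerations):** target difference 2 NRS units, two-sided alpha 0.05, power 0.80, 25 per group. **Assumed, because the document gives no figure:** the share p of patients receiving one of the drugs, and the difference g between the drugs in NRS at the primary measurement (0.5 to 2 units).

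**1. The plan's own figure.** No standard deviation is given, so 25 per group cannot be reproduced directly. Solving backwards for 80% power with a two-sample t-test gives an SD of about 2.47 (2.52 by the normal approximation). The standard error of the treatment difference is then 2.47 × √(2/25) = 0.70.

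**2. Chance imbalance.** The number per arm on one drug is Binomial(25, p), independently in each arm. A 20-point imbalance is 5 patients.

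| Split | P(at least 20 points) | P(at least 28 points) |
|---|---|---|
| 50/50 | 20% | 6.5% |
| 30/70 | 16% | 4.4% |
| 20/80 | 11% | 2.1% |
| 10/90 | 3% | under 1% |

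**3. Effect of an imbalance.** The shift in the treatment difference is imbalance × g. At 20 points:
- g = 0.5: 0.2 × 0.5 = 0.1 unit, or 0.14 standard errors (0.1/0.70)
- g = 1: 0.2 units, or 0.29 standard errors
- g = 2: 0.4 units, or 0.57 standard errors

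**4. Precision.** The drug difference contributes variance g² × p(1 − p). With p = 0.5 and a total SD of 2.47 (variance 6.10), its share is 0.25/6.10 = 4% for g = 1 and 1.00/6.10 = 16% for g = 2. At 10/90 the shares fall to 0.09/6.10 = 1.5% and 0.36/6.10 = 5.9%.

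At 50/50, the residual SD after adjustment is √(6.10 − 0.25g²): 2.457, 2.419 and 2.259 for g = 0.5, 1 and 2. t-test power at 25 per group follows. The unstratified column averages over the chance imbalances in step 2.

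| g | Planned t-test | Stratified and adjusted for drug | Adjusted for drug, unstratified |
|---|---|---|---|
| 0 | 80.1% | 80.1% | 79.2% |
| 0.5 | 80.1% | 80.5% | 79.6% |
| 1 | 80.1% | 81.7% | 80.9% |
| 2 | 80.1% | 86.6% | 85.8% |

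If 2.47 is instead the SD within each block drug, the planned t-test has 79.7%, 78.5% or 73.9% power for g = 0.5, 1 or 2.

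**The case against.** The strongest case against has four parts.

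*An unadjusted comparison is valid.* This stands. Randomisation balances block drug in expectation, and the t-test's standard error already contains the between-drug variance. A reader might infer that the mixed block biases the result. The document does not support that: an imbalance here is ordinary sampling error.

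*The effect is assumed.* This stands too. Scientific Background gives one block duration, 12 to 14 hours, with no split by drug. A difference of 1 to 2 units between the two drugs would equal the protocol's whole range for a minimum clinically important difference, which is why smaller values are shown.

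*Scoring each patient at their own block resolution absorbs part of the problem.* Partly right: a longer block moves the clock time, not the block state at scoring. Time since the study injection still varies, and the 24-hour definition offers no such protection.

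*Other factors vary as well*, such as primary or revision repair and three or four portals. True, but those do not define the moment of the primary measurement.

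Three further inferences are tempting and go beyond the text:
- That the drug is chosen patient by patient. Only the volume is described so; the drug could follow supply or habit.
- That the block is complete before the study solution reaches the operating room. Only block before injection is supported.
- That a planned safety comparison mixes different bupivacaine totals. At 5 mg/ml the block adds 75 to 100 mg, so active patients receive 266 mg, or 341 to 366 mg, of bupivacaine depending on block drug. However, Study Objectives says only that such events will be recorded and specifies no comparison of them.

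**Conclusion.** The point holds as one of balance and precision, not of validity. The protocol permits two block drugs without a selection rule, ties its primary score to that block, and uses block drug in neither allocation nor analysis.

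The size is modest. An imbalance of 20 points or more has a probability between 3% and 20%, depending on the split, and moves the treatment difference by 0.1 to 0.4 units. Recoverable power is under half a point if the drugs differ by 0.5 units, about 1.6 points at 1 unit and about 6.5 points at 2 units, all at a 50/50 split and an implied SD of 2.47. If one drug dominates, the issue largely disappears. The split, the drug effect and the SD are all assumptions. The change is worth making because stratified adjustment costs almost nothing even if the drugs do not differ.

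**What to change.** - State that block drug and volume are recorded for every patient and reported by arm.
- Have the anaesthesiology team declare the intended block drug to the pharmacy before the randomisation number is assigned. Stratify the list by it, with restricted allocation inside each stratum; two unrestricted lists would not improve balance.
- Replace the primary t-test with a linear model containing arm and block drug (the declared drug where randomisation is stratified by it).
- If randomisation has begun, leave allocation alone and pre-specify adjustment for block drug only, before unblinding.
- Do not add volume to the model. Unstratified adjustment for drug and volume together breaks even only if the drugs differ by about 1 unit. Nor is a split of adverse events by block drug needed.
- Reconcile the two definitions of the primary outcome, since the role of the block differs between them.

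**Cost:** one field on the pharmacy request, a second randomisation list, and one degree of freedom. If randomisation is unstratified and the drugs do not differ, power falls by at most about 1 percentage point (80.1% to 79.2%). No change to block care is implied.

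### No pain score is planned before the block and study injection, and pain is compared by unadjusted t-test; the comparison is unbiased, but the trial may forgo some precision.

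*Combined protocol and SAP*

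**What the plan says.** Study Design and Methods puts the patient with the team before any treatment: "Patients will provide written consent for participation on the day of surgery". The steps then described are randomisation, interscalene block, surgery and study injection. The first pain score appears only after these: "At the conclusion of surgery, patients will be taken to PACU, where they report their NRS pain score". The primary score is asked for at the next-day call and refers back to the moment when the patient felt the block had fully gone. Study Objectives describes the primary outcome as pain at 24 hours. On either description it is a single post-operative score with no earlier value to set beside it.

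Statistical Considerations says that continuous measures, pain scores among them, "are presented as mean \pm standard deviation, and compared using t-tests". It names no covariate. It refers to some demographic information but does not list pre-operative pain. The size of the trial is justified "with a two-tailed significance level of 0.05 and a power of 0.8, a sample size of 50 is required, 25 in each group", for a difference described thus: "We chose a change in the score of 2 units to represent a clinically important improvement in pain control".

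Eligibility Criteria admits both primary and revision repairs. It excludes patients who already have chronic shoulder pain, and also "opioid use for greater than 30 days preoperatively".

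**The concern.** Patients may arrive with different amounts of shoulder pain, and the plan does not record it. With 25 per arm, the standard error of a difference in baseline means is sqrt(2/25) = 0.28 SD, so a noticeable chance difference in starting pain is possible. Without a pre-treatment score, such a difference can be neither described nor adjusted for.

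If starting pain predicts the primary score, adjusting for it removes part of the residual variance and narrows the confidence interval without enrolling anyone else. What is at stake is efficiency and description of the sample, in a small trial planned at exactly 80% power.

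**Working it through.** **Inputs from Statistical Considerations.** Difference 2 NRS units; two-sided alpha 0.05; power 0.80; 25 per arm.

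**Inputs not in the documents (assumptions).** The SD of the primary score, and the correlation r between a pre-operative score and the primary score. I take r from 0 to 0.5.

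**Step 1: the plan's own figure.** The total of 50 cannot be reproduced directly because no SD is given. It can be inverted.

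- Normal approximation: n per arm = 2 × (1.960 + 0.842)² × SD² / 2². Setting n = 25 gives SD = 2.52.
- t-test (noncentral t, 48 df): 80.0% power at 25 per arm gives SD = 2.47.

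So 50 patients is consistent with an SD of about 2.5. I use 2.47, which makes the unadjusted power 80% by construction. The standard error of the arm difference is 2.473 × sqrt(2/25) = 0.70, and the expected 95% half-width is 1.41 units.

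**Step 2: adjustment for one baseline score.** The residual variance is multiplied by (1 − r²). Estimating the slope has a price: with 50 patients and a normally distributed covariate, the variance of the adjusted difference rises on average by a factor 1 + 1/(50 − 4) = 47/46. The net variance factor is

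V = (1 − r²) × 47/46,

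with 47 residual df. Power comes from the noncentral t distribution with noncentrality 2 / (2.473 × sqrt(V) × sqrt(2/25)). The equivalent unadjusted total sample size is 50/V.

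| r | V | Power for 2 units | 95% half-width | Equivalent total N |
|---|---|---|---|---|
| t-test as planned | 1 | 80.0% | 1.41 | 50 |
| 0 | 1.022 | 79.1% | 1.42 | 49 |
| 0.2 | 0.981 | 80.7% | 1.39 | 51 |
| 0.3 | 0.930 | 82.7% | 1.36 | 54 |
| 0.4 | 0.858 | 85.6% | 1.30 | 58 |
| 0.5 | 0.766 | 89.2% | 1.23 | 65 |

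**Step 3: break-even.** V = 1 when 1 − r² = 46/47, so r = sqrt(1/47) = 0.146. At r = 0.15 power is 80.0%, the same as for the t-test; below that, adjustment loses slightly.

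**Step 4: why not a change score.** If the baseline and outcome SDs are equal, the change has SD 2.473 × sqrt(2(1 − r)). That is 3.50 at r = 0, 2.93 at r = 0.3 and 2.47 at r = 0.5, giving power of 51%, 66% and 80%. Subtracting the baseline therefore does worse than ignoring it whenever r is below 0.5.

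**The case against.** The best objection is that the gain may be nil. The documents report no correlation, and there are reasons to expect a low one. Excluding patients with chronic shoulder pain may narrow the spread of pre-operative scores. The outcome is also a different quantity: acute surgical pain at the end of the block, recalled by telephone. This objection stands. It is why the table starts at zero, and why the plan can only be said possibly to forgo precision. It does not remove the case for asking, because the worst outcome is a loss of about 1 point of power.

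A reader might infer three stronger things, and the documents support none of them.

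- *That the planned comparison is biased.* Allocation is by computer-generated number, and the t-test's standard error already allows for chance differences in starting pain. The loss is of precision.
- *That the comparison of chronic pain lacks a starting value.* Patients with chronic shoulder pain are excluded at entry, and the outcome is a new event, namely chronic pain leading to specialist referral. Eligibility supplies the starting state.
- *That prior opioid use should also be a covariate, for morphine equivalents.* Up to 30 days of prior use is allowed, so exposure may vary, but nothing in the documents lets the benefit of adjusting be quantified.

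**Conclusion.** The gap is real: no score is planned before the block and injection, and the analysis has no baseline covariate. It is a missed opportunity for efficiency and description, and the validity of the randomised comparison is not in question. Adding a pre-operative score as a covariate would change power by about −1 point at zero correlation, by +1 to +3 points at 0.2 to 0.3, and by +6 to +9 points at 0.4 to 0.5.

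These figures rest on an SD back-solved from the stated sample size, on correlations that are assumed throughout, and on all 50 patients contributing data. The improvement is cheap and worth making, but its size is unknown and could be zero.

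**What to change.** In Study Design and Methods, add: *After consent on the day of surgery, and before randomisation and the interscalene block, record shoulder NRS at rest.*

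In Statistical Considerations, replace the t-test for pain scores with a pre-specified linear model containing arm and pre-operative NRS, reporting the adjusted arm difference with its 95% confidence interval. State that the outcome is the post-operative score itself and not the change from baseline. Both parts are needed: the question brings no precision unless the model that uses it is fixed in advance.

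Keep the total at 50. The correlation is unknown, so the covariate should not be used to justify fewer patients.

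The cost is one question at a contact that already takes place, one term in the SAS model, one degree of freedom, and about 1 point of power if the pre-operative score turns out to be unrelated to the outcome.

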Official Study Title: Use of liposomal bupivacaine for postoperative pain management after arthroscopic rotator cuff repair

ClinicalTrials.GOV ID Number: NCT03149887

Protocol Date: 2/13/2019

Scientific Background:

Arthroscopic rotator cuff repair is among the most painful of orthopedic surgeries. Hundreds of thousands of these procedures are carried out in the U.S. each year. Many involve the use of a brachial plexus nerve block, which serves to control pain for 12 to 14 hours. However, when the block wears off, many patients are left with severe pain. This severe pain is must then be managed at home with oral opioids, which have numerous undesirable side effects, and may lead to chronic opioid dependence. Thus, any therapy which might reduce the pain burden on these patients and therefore reduce opioid use and side effects, would be advantageous.

Recently, a long-acting form of bupivacaine, prepared in liposomes, has been approved for use by injection in the surgical field, though not for peripheral nerve blockade. The drug has been used to improve postoperative pain after total knee arthroplasty and total hip arthroplasty when injected in the peri-articular tissues by the orthopedist, as well as in other surgeries, both orthopedic and non-orthopedic. Liposomal bupivacaine is FDA approved for administration into the surgical site to produce postsurgical analgesia and mitigate pain, but it hasn't been yet used for rotator cuff surgery.

Study Objectives:

The purpose of this research study is to determine if liposomal bupivacaine, injected into the surgical field during rotator cuff repair surgery provides superior analgesia post operatively (after the standard nerve block resolves) compared with standard therapy.

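### If pain at block resolution is the primary outcome, it is obtained only by recall at a next-day call, and one timed diary line would avoid this cheaply

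*Combined protocol and SAP*

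**What the plan says.** The plan describes the primary outcome in two ways. Study Objectives states: "The primary outcome measure is pain score at 24 hours, which will be obtained by phone follow up". Study Design and Methods describes the call: "Patients are to be called the day after surgery (approximately 24 hrs after leaving the hospital), and asked about their pain experience". It then specifies that "for the primary outcome, they will be asked to relate NRS pain score, at the time that the interscalene block had, in their perception, completely" lifted. Resolution is defined by three signs together: "restoration of hand sensation, movement at elbow, and onset of pain at the shoulder". Statistical Considerations sizes the trial on a 2-unit NRS reduction at block resolution, which matches the Methods and not the Objectives.

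On timing, Scientific Background describes a "brachial plexus nerve block, which serves to control pain for 12 to 14 hours".

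On the diary, Study Objectives says "patients will keep a pain diary, documenting pain scores and opioid use for the first 72 hours", and the Methods gives it a limited role: "For the secondary analyses of pain and opioid use, patients will record their NRS scores in a 72 hour postoperative diary". Neither section states when or how often entries are made, and neither asks for an entry when the block wears off.

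The plan has no rule for a patient whose block has not resolved by the call: no second call, no substitute source and no missing-data rule.

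**The concern.** Under the Methods definition, the endpoint for which the trial is sized is a momentary pain score that the patient must remember and report many hours later, with opioid use and further pain possibly intervening. A score noted at the time would not depend on memory. Patients already have an NRS diary covering those hours, so the means of recording it are nearly in place.

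Two things are at stake. The first is measurement error in the primary outcome. The trial has 25 per group, and its design effect equals its threshold for clinical relevance (2 units), so there is little slack for extra variance. The second is a gap in the definition. A patient who has not shown all three signs by the call has no value to give. Because onset of shoulder pain is one of the signs, and the study drug is meant to reduce pain after the block, any such gap could differ by arm.

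**Working it through.** **Recall interval.** Inputs: call 24 h after leaving hospital (Study Design and Methods); block duration 12 to 14 h (Scientific Background); hours from block to leaving hospital, L, not stated.

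Interval = L + 24 − (12 to 14).

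| L (h) | Status | Interval (h) |
|---|---|---|
| 0 | lower bound, since surgery and PACU intervene | 10 to 12 |
| 4 | assumed | 14 to 16 |
| 6 | assumed | 16 to 18 |
| 8 | assumed | 18 to 20 |

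**The plan's sample size.** Inputs: difference 2, two-sided alpha 0.05, power 0.80, 25 per group, t-test. No SD is given, so the total of 50 cannot be reproduced directly. Solving for the SD instead:

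- Normal approximation: SD = 2 × √(25/2) / (1.960 + 0.842) = 7.071 / 2.802 = 2.52.
- Exact t-test power: SD = 2.47.
- Check with SD 2.5: total N is 50 (normal approximation) or 52 (t-test).

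An SD of about 2.5 is therefore consistent with the plan, but it is inferred.

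**Effect of recall noise (illustration).** Independent recall error with SD e gives a total SD of √(2.47² + e²). The values of e are assumptions. T-test power uses 25 per group and a true difference of 2.

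| e | Total SD | Power |
|---|---|---|
| 0 | 2.47 | 80% |
| 0.5 | 2.52 | 78% |
| 1.0 | 2.67 | 74% |
| 1.5 | 2.89 | 67% |

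**Block unresolved at the call.** With L of 4 to 8 h, the call falls 28 to 32 h after the block. That is at least twice the stated duration (28/14 = 2), so few patients should be affected. If 1, 2 or 3 of the 25 active-arm patients had no value (assumed counts), power would be 79%, 78% or 77%, apart from any selection effect.

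**The case against.** Several stronger readings are tempting, and the documents do not support them.

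*That a better, real-time measurement already exists and is being ignored.* The documents do not say this. Diary entries could be once-daily and themselves recalled, which would be enough for the maximal daily scores among the secondary outcomes. The diary helps only if a timed item is added.

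*That the problem exists whichever primary time point is kept.* It does not. If the 24-hour score in Study Objectives is primary, a current score given at the call needs little recall and the point falls away. The conflict between sections comes first.

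*That recall shrinks the treatment effect below 2 units.* If a fraction w of the recalled score reflected pain at the call, and the arms no longer differed then, a true difference of 2 would be observed as 2 × (1 − w), or 1.8 to 1.4 for w of 0.1 to 0.3. Both the weights and the equality of arms at the call are assumptions, and the second sits badly with Study Objectives, which looks for a difference at 24 hours. Starting from exactly 2, any attenuation falls below 2, so crossing the threshold is not evidence. With blinded patients, noise is more plausible than a systematic difference between arms.

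*That late resolvers are expected in number.* The sentence "Any adverse occurrences related to nerve blockade or prolonged bupivacaine effect will also be recorded" concerns safety recording. It does not say that blocks will outlast the call.

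Two further objections have force. The unstated planning SD may already include recall error, in which case the power loss is smaller or nil. Also, the 12 to 14 h figure is for pain control, while the definition requires sensory and motor return as well; later resolution would shorten the interval.

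What stands is that the Methods score is retrospective by many hours on the plan's own figures, nothing else captures it, and an unresolved block is not provided for.

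**Conclusion.** The point holds conditionally and is minor. It depends on block resolution being the primary time point, as the Methods and the sample size have it. The 10 to 12 hour lower bound follows from the plan's figures, taking the block to end at 12 to 14 hours; the 14 to 20 hour range also needs the assumed time to discharge. The likely consequence is extra noise. Power of 78% to 67% illustrates it, resting on a back-solved SD and assumed error SDs. It is not an estimate of what will happen, and bias in a known direction is not shown. The missing-value gap is real but probably affects few patients. The case for acting is that the remedy is cheap, not that the endpoint is unusable.

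**What to change.** 1. Reconcile Study Objectives, Study Design and Methods, and Statistical Considerations on one primary time point.
2. If block resolution is kept, add one line to the diary for the clock time and NRS score when the block wore off, to be completed at that moment. At the postoperative day 1 call, blinded staff ask the patient to read it out and record it.
3. Use the recalled score only when the line is blank, flag it, and run a sensitivity analysis by source of the score.
4. If the block has not resolved at the call, the patient completes the line later. Blinded research staff, not the unblinded surgeon, then take the value from the returned diary. Study Objectives has the surgeon collecting the diary and the Methods has the research team doing so; these statements should be aligned on the research team.

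Cost: one diary line, an amended call script and a short addition to the analysis text, with no extra visit, call or staff. The downside is real but limited. Some lines will be blank, for instance when a patient is asleep, possibly in a way related to pain. The endpoint will then mix noted and recalled scores, which is why the flag and the sensitivity analysis are needed.
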